9.4.6. Health Care Resource Utilization

Category	Variable	Timepoint
Inpatient hospitalizations (including specialty wards, ICU, ER, general medicine ward, or other)	
Inpatient hospitalization occurring after index treatment initiation
 
 • Yes; • No; • Unknown. 
Primary reason for hospitalization:
 
 • Invasive aspergillosis or mucormycosis disease monitoring; • Other disease monitoring; • AE related to invasive aspergillosis or mucormycosis; • Other (specify); • Unknown. 
Location for inpatient hospitalization:
 
 • Oncology ward; • Hematology ward; • Transplantation ward; • ICU; • ER; • General medicine ward; • Other ward (specify); • Unknown. 
Use of a mechanical ventilator:
 
 • Yes; • No; • Unknown. 	Post-index period

Category	Variable	Timepoint
	
Discharge date (DD MMM YYYY)
 
Discharge location (if applicable):
 
 • Transferred to another ward for inpatient care; • Discharged to home or self-care (routine discharge); • Discharged to long term care facility/hospice; • Not applicable; • Other (specify); • Unknown. 	
Outpatient visits (not associated with a hospital stay)	
Outpatient visit/referral occurring after index treatment initiation:
 
 • Yes; • No; • Unknown. 	Post-index period
	
Health care professional visit or referral:
 
 • Primary care visit (general practitioner); • Secondary care visit (specialist); • Secondary care referral (specialist); • ER visit. 	
	
Primary reason for visit/referral:
 
 • Planned visit/referral for invasive aspergillosis or mucormycosis disease monitoring; • Unplanned visit/referral for invasive aspergillosis or mucormycosis disease monitoring; • Planned visit/referral for other disease monitoring; • Unplanned visit/referral for other disease monitoring; • Unplanned visit/referral for AE related to invasive aspergillosis or mucormycosis; • Other; • Unknown. 	
	
Type of health care professional:
 
 • Infectious disease specialist; 	

Category	Variable	Timepoint
	
 • Oncologist; • Hematologist; • General internist; • Gastroenterologist; • Cardiologist; • Obstetrician/gynecologist; • Neurologist; • Radiologist; • Dermatologist; • Psychiatric; • Surgeon; • Specialty nurse; • Other (specify); • Unknown. 	
	Date of outpatient visit/referral (DD MMM YYYY)	

AE = adverse event; ER = emergency department; ICU = intensive care unit.

9.5. Study Size

As the study is primarily descriptive in nature, formal sample size calculations are not required. Given the rarity of invasive aspergillosis and mucormycosis, we will include all eligible patients identified from sites, up to a target sample size of 600 patients.

Table 1 shows the width of the CI that can be obtained from different sample sizes. Precision estimates were generated based on the all-cause mortality rate at day 42 for patients with invasive aspergillosis who received isavuconazole in the SECURE trial.⁴ These estimates suggest that a sample size of 150 to 200 patients initiating isavuconazole would be expected to yield a reasonable margin of error (between 5.00% and 6.25%) for estimating a 95% CI for the mortality rate; thus, an overall sample size of up to 600 patients would yield a reasonable margin of error. However, 95% CIs may be wider for analyses of rare events or analyses conducted in small subgroups.

Table 1. Wilson 95% CI Based on All-Cause Mortality Rate at Day 42 for Patients With Invasive Aspergillosis Who Received Isavuconazole in the SECURE Trial

	Sample Size (N)	95% CI Width
All-cause mortality rate at day 42 in SECURE trial = 19%	292	9.0
	237	10.0
	152	12.5
	106	15.0

CI = confidence interval.

Because mucormycosis is rare, sample size for this population is expected to be low and limited by the availability of patient medical records at sites; therefore, all eligible patients will be included. Based on the observed weighted all-cause mortality rate of 33% in the sample of mucormycosis patients (n = 37) in the VITAL trial, such a sample would allow to estimate the mortality rate within a precision of 15%.

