- **Pre-index event period:** Baseline data on demographics and medical history will be collected based on all available information in medical records before the index event.
- **Post-index event period:** The timeframe for follow-up data collection will begin one day post-index treatment initiation and end at the earliest of the following: six-months post-index treatment discontinuation, death, loss to follow-up, or December 31, 2019. Key timepoints of interest for assessment of clinical outcomes (mortality and overall response), and safety will be assessed at 6 weeks, 12 weeks, and 24 weeks after initiation of index treatment.

Variables: Categories to be abstracted from the medical records if available include, but are not limited to, the following:

- Demographic, medical history, and clinical characteristics (eg, age, sex, history of invasive fungal infection and prior antifungal treatments, fungal disease characteristics such as diagnosis, mycological confirmation, date of diagnosis, and other comorbidities including underlying illness/risk factors for invasive aspergillosis and mucormycosis).
- Clinical outcomes (eg, overall response [including clinical response, mycological response, radiological response], and mortality).
- Safety outcomes (AEs and SAEs).
- Isavuconazole treatment patterns (eg, formulation, dosage [loading and maintenance], duration, treatment changes (including dosage adjustments, switching, and discontinuation), and concomitant medication).
- Health care resource utilization (eg, length of stay [LOS], emergency room [ER] visits, intensive care unit [ICU] visits and LOS, inpatient hospitalizations, and planned and unplanned outpatient visits).

Study size: Precision estimates were generated based on the all-cause mortality rate at day 42 for patients with invasive aspergillosis who received isavuconazole in the SECURE trial.⁴ A sample size of 150 to 200 patients is expected to yield a reasonable margin of error (between 5.00% and 6.25%) for estimating a 95% confidence interval (CI) for the mortality

^d The eligibility period end date is subject to change based on timing of medical record abstraction and anticipated number of potentially eligible patients during the proposed eligibility timeframe.

rate. However, 95% CIs may be wider for analyses of rare events or analyses conducted in small subgroups.

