9. RESEARCH METHODS

9.1. Study Design

This is an observational retrospective cohort study involving the review and abstraction of pertinent data from the medical records of patients diagnosed with invasive aspergillosis or mucormycosis who received treatment with isavuconazole (index event) between October 15, 2015, and June 30, 2019.^f The target sample size for this study is approximately 600 patients (with a minimum of 200) across 22 sites located in Europe.^g

De-identified data (ie, anonymous to non-site staff) on patient demographics, disease characteristics, isavuconazole treatment patterns, clinical response, safety outcomes, and HCRU will be collected from patient medical records and entered into an EDC system by site staff between August 2020 and March 2021 for Germany, Spain, and the UK, and between October 2021 and January 2022 for Italy.^h The differences in the data abstraction timelines are due to ethics and contracting processes in Italy taking between 6 to 12 months to complete, compared with an estimated maximum of 4 months in the remaining countries. As this study is retrospective, information pertaining to patient care will already be documented in patient medical records at the time of chart abstraction.

A steering committee composed of experts within hematology and infectious diseases will provide input and guidance on the study design and implementation, as well as the interpretation of results.

^f The eligibility period end date is subject to change based on timing of medical record abstraction and anticipated number of potentially eligible patients during the proposed eligibility timeframe.

^g Dependent on interest in participation and the number of eligible patients each site can contribute, the total number of sites enrolled as well as patients per site could increase/decrease.

^h Dates of medical record abstraction are subject to change based on the volume of potentially eligible patients during the timeframe of the current eligibility period and the timing of study start-up.

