9.2. Setting

9.2.1. Study Sites

A feasibility assessment was conducted, and a total of 22 sites meeting the study criteria were identified: 6 in Germany, 5 in Italy, 5 in Spain, 4 in the UK, and 2 in France. All sites are hospital-based facilities and had access to eligible medical records of patients treated within oncology, hematology, and/or transplantation wards and ICUs. During this feasibility assessment, sites were evaluated on the following parameters, to determine their suitability for participation:

- Number of eligible patients treated with isavuconazole for either invasive aspergillosis or mucormycosis.
- Location of medical records and continuity of data across wards and staff resources, to be able to abstract the required data.
- Frequency and availability of follow-up data.

The total number of sites who participate in the study may differ from the anticipated number (22), depending on a site's interest and the availability of its staff (considering the COVID-19 pandemic), and access to eligible medical records. The sites will be hospital based; thus, the patient population will consist of those who were either hospitalized or attending a hospital at the initiation of isavuconazole therapy. As invasive aspergillosis and mucormycosis are rare fungal infections, we expect that the pool of potential patients across sites will be small. The total number of patients eligible patient records to which the sites have access was estimated to be about 583.

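### The 5.00% margin of error quoted for 150 to 200 patients belongs to 237 patients in Table 1; at 19% mortality, 200 patients give about 5.4%

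*Protocol*

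**What the plan says.** Protocol section 9.5 bases its precision on the SECURE day-42 result, given in the table as "All-cause mortality rate at day 42 in SECURE trial = 19" per cent. It introduces the table with "Table 1 shows the width of the CI that can be obtained from different sample sizes", so the entries are full widths and the margin of error is half of each. The table is titled "Wilson 95% CI Based on All-Cause Mortality Rate at Day 42 for Patients With Invasive Aspergillosis" and continues with the SECURE isavuconazole arm. It has four rows:

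| N | Full 95% CI width (points) | Half-width (points) |
|---|---|---|
| 292 | 9.0 | 4.50 |
| 237 | 10.0 | 5.00 |
| 152 | 12.5 | 6.25 |
| 106 | 15.0 | 7.50 |

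The half-width column is added here. There is no row for 200.

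The text then presents the following as what these estimates show: "a sample size of 150 to 200 patients initiating isavuconazole would be expected to yield a reasonable margin of error (between 5.00% and 6.25" per cent). It goes on to call the margin for up to 600 patients reasonable as well, without giving it. The abstract carries the same range: "A sample size of 150 to 200 patients is expected to yield a reasonable margin of error (between 5.00% and 6.25" per cent).

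Section 9.1 sets the study size at "approximately 600 patients (with a minimum of 200) across 22 sites located in Europe". Section 9.2.1 reports that the number of eligible records at the sites "was estimated to be about 583". SAP section 2.1 repeats the target and the minimum but not the margins.

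**The concern.** The margins in the sentence are exactly the half-widths of two rows of Table 1, but they are attached to different sample sizes. Moving from 152 to 150 is ordinary rounding. Moving from 237 to 200 is not, and the margin is printed to two decimals. The text and its own table therefore disagree about how many patients a 5.00% margin needs.

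All-cause mortality is a primary outcome, and this paragraph is the protocol's only quantitative support for the size of the invasive aspergillosis sample. The figure of 200 is also the stated minimum for the study, so a reader may well take 5.00% as the precision available at that minimum. A reader of the abstract alone has no table to check it against.

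**Working it through.** **Inputs.** Mortality p = 0.19 (section 9.5, Table 1). Confidence level 95%, so z = 1.96 and z² = 3.8415. Day-42 status is assumed known for every patient.

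**Formulas for the half-width h.**

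- Wald: h = z·√(p(1−p)/n), with p(1−p) = 0.19 × 0.81 = 0.1539.
- Wilson: h = z·√(p(1−p)/n + z²/(4n²)) / (1 + z²/n).

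**Step 1: reproduce Table 1.** For Wald, the N needed is z²·p(1−p)/h² = 0.5912/h², rounded up:

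- h = 0.045: 0.5912/0.002025 = 291.95, so 292
- h = 0.050: 0.5912/0.0025 = 236.5, so 237
- h = 0.0625: 0.5912/0.00390625 = 151.3, so 152
- h = 0.075: 0.5912/0.005625 = 105.1, so 106

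These are the table's four values. The smallest N by the Wilson formula is 291, 236, 150 and 104. The table is labelled Wilson but matches Wald; the difference is at most two patients, and no change is asked for on that account. The table is sound.

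**Step 2: check the 150 end.**

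- Wald: 1.96 × √(0.1539/150) = 6.28%.
- Wilson: 1.96 × √(0.001026 + 0.0000427) / 1.0256 = 6.25%.

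The stated 6.25% is right.

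**Step 3: check the 200 end.**

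- Wald: 1.96 × √(0.1539/200) = 1.96 × 0.02774 = 5.44%, full width 10.87.
- Wilson: 1.96 × √(0.0007695 + 0.0000240) / 1.0192 = 5.42%, full width 10.83, interval 14.2% to 25.0%.
- Other methods at n = 200: Agresti-Coull 5.45%, Clopper-Pearson 5.66%, Wilson with continuity correction 5.66%.

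No method gives 5.00%.

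**Step 4: find where 5.00% does hold.** At n = 237 the half-width is 4.98% (Wilson) or 4.995% (Wald). The smallest N is 236 (Wilson) or 237 (Wald), about 18% above 200 (236/200 = 1.18). Alternatively, with n held at 200, Wald needs p(1−p) = 0.0025 × 200/3.8415 = 0.1302, that is p = 15.4%; Wilson also gives 15.4%. The protocol's rate is 19%.

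**Step 5: larger samples at the same 19%.** At the 583 records found in feasibility the half-width is 3.18% by either method. At 600 it is 3.13% (Wilson) or 3.14% (Wald).

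**The case against.** The arithmetic is not in dispute. The strongest reply is about reading. The sentence says that the margins for 150 to 200 patients lie between two values; it does not say that 200 patients give 5.00%. By the Wilson formula the margin falls from 6.25% at 150 to 5.42% at 200, so every value is inside the quoted range. This does not rescue the sentence. It claims to report the table's estimates, both of its ends are half-widths from that table, and one end is paired correctly with its sample size. The natural reading pairs the other end with 200. Even on the loose reading, the lower bound is not reached anywhere in the stated range.

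Other points stand in part:

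- **Consequences.** Section 9.5 says that no formal sample size calculation is needed and that all eligible patients are taken up to 600. Feasibility found about 583 records, well above 237. Nothing operational turns on the figure. This is right, and it is why the point is small.
- **The minimum of 200.** It covers both diseases, whereas 19% is an invasive aspergillosis rate; section 9.5 uses 33% for mucormycosis. The 5.4% therefore applies to 200 patients with 19% mortality. If all 200 had 33% mortality, the Wald margin would be 1.96 × √(0.33 × 0.67/200) = 6.5%. The documents do not give the disease mix, so the true value for a mixed group of 200 lies somewhere between. This qualifies the link to the study minimum but does not bring 5.00% back.
- **The figure at 600.** The same caution applies: 3.1% at 19% mortality, against 1.96 × √(0.2211/600) = 3.8% at 33%. Leaving it out is not an error, and adding it is optional.

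**Conclusion.** The concern holds. The 5.00% end of the range is wrong as written in section 9.5 and in the abstract: it belongs to about 237 patients, not 200. At 19% mortality, 200 patients give a margin of about 5.4%, so the precision there is overstated by about 0.4 percentage points. The 6.25% end and Table 1 itself are correct.

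This rests on the protocol's own 19%, on a 95% two-sided interval for a single proportion, and on complete day-42 status. It does not depend on the choice between Wilson and Wald. The practical effect is small, because the study tests no hypothesis and no enrolment rule or analysis uses the figure. It should still be corrected, since it misstates the precision for a primary outcome and contradicts the table that it cites.

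**What to change.** In section 9.5 and in the study-size paragraph of the abstract, make one of two changes:

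- keep 150 to 200 patients and give the margin as between about 5.4% and 6.25%; or
- keep 5.00% to 6.25% and give the sample size as about 152 to 237 patients, as in Table 1.

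Optionally, replace the unquantified remark about 600 patients with a margin of about 3.1%, stating that this assumes 19% mortality throughout.

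The cost is one wording change in two places, and with the first option a slightly less favourable stated precision at 200. No patients are added and no analysis changes; the SAP needs no edit because it does not carry the margins. Section 10.4 requires ethics approval of protocol amendments, so the correction is sensibly combined with another amendment. If none is planned, the study report can state the corrected figure.

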9.6. Data Management

9.6.1. Case Report Forms

Screening results for inclusion and exclusion criteria will be captured in the EDC system for all patients in the initial target cohort.

As used in this protocol, the term CRF should be understood to refer to an electronic data record.

A CRF is required and should be completed for each included patient.

In this study, the clinical research organization (CRO) will provide a password-protected, web-based EDC system to serve as an integrated, transparent tool to collect and manage data and track study progress at the center and at the patient level. Data in the EDC system will be kept in a central location and all data will be transmitted to a central database.

The completed original CRFs are the sole property of Pfizer and should not be made available in any form to third parties, except for authorized representatives of Pfizer or appropriate regulatory authorities, without written permission from Pfizer. The investigator shall ensure that the CRFs are securely stored in encrypted electronic form and will be password protected to prevent access by unauthorized third parties.

The investigator has ultimate responsibility for the collection and reporting of all clinical, safety, and laboratory data entered on the CRFs and any other data collection forms (source documents) and ensuring that they are accurate, authentic/original, attributable, complete, consistent, legible, timely (contemporaneous), enduring, and available when required. The CRFs must be signed by the investigator or by an authorized staff member to attest that the data contained on the CRFs are true. Any corrections to entries made in the CRFs or source

documents must be dated, initialed, and explained (if necessary) and should not obscure the original entry.

The investigator also has ultimate responsibility for ensuring that data entered are accurate, authentic/original, attributable, complete, consistent, legible, timely (contemporaneous), enduring, and available when required. The investigator or authorized staff member must attest that the data entered in the EDC are true.

The source documents are the hospital or the physician's chart. In these cases, data collected on the CRFs must match those charts.

Site staff will be trained by the CRO to perform the medical record abstraction, including data entry and how to retrieve and respond to data queries in the EDC system. To participate in this study, all sites must be able to access the EDC system and complete data entry into the CRFs via the EDC system.

The EDC system will include logic checks to minimize data entry errors. Data inconsistencies outside the logic checks will be managed by manual queries issued by data management within the EDC system for site completion. All queries will be monitored until resolution within the EDC through the electronic query report.

9.6.2. Record Retention

To enable evaluations and/or inspections/audits from regulatory authorities or Pfizer, the investigator agrees to keep records, including the identity of all participating patients (sufficient information to link records, eg, CRFs and hospital records), all original signed informed consent/assent documents (if applicable), safety reporting forms, source documents, detailed records of treatment disposition, and adequate documentation of relevant correspondence (eg, letters, meeting minutes, and telephone call reports). The records should be retained by the investigator according to local regulations or as specified in the clinical study agreement (CSA), whichever is longer. The investigator must ensure that the records continue to be stored securely for so long as they are retained.

If the investigator becomes unable for any reason to continue to retain study records for the required period (eg, retirement, relocation), Pfizer should be prospectively notified. The study records must be transferred to a designee acceptable to Pfizer, such as another investigator, another institution, or to an independent third party arranged by Pfizer.

Study records must be kept for a minimum of 15 years after completion or discontinuation of the study, unless the CRO and Pfizer have expressly agreed to a different period of retention via a separate written agreement. Record must be retained for longer than 15 years if required by applicable local regulations.

The investigator must obtain Pfizer's written permission before disposing of any records, even if retention requirements have been met.

9.7. Data Monitoring

The CRO will supervise and monitor de-identified data abstraction by site staff into the EDC system.

Quality-control mechanisms (eg, verification of data completeness, validations, and edit checks), which will be automated at the time of data entry, will be built into the EDC. Queries will be generated by the CRO for resolution by site staff within the EDC system.

9.8. Data Cleaning

The EDC system will have built-in methods for data validation (eg, drop-down lists, value range controls, and standardized response formats). However, a data cleaning method will furthermore be employed to correct inconsistencies or errors that were not captured during data entry (eg, outliers or conflicting data). Data will be generated for site resolution. The CRO will follow up on the identified data queries until they are resolved by the site.

9.9. Data Analysis

This study is primarily descriptive in nature. Categorical variables will be reported as counts (n) and frequencies (%). Continuous variables will be reported using mean, standard deviation, median, minimum and maximum, interquartile range, and range. Time to event outcomes will be assessed using the KM method and will be reported as descriptive statistics (eg, median time to event) with 95% CI. Results will be presented for the overall group (both disease types) and separately for invasive aspergillosis and mucormycosis.

The statistical analysis plan (SAP) will provide a detailed description of analytic populations, analyses to be performed, and methods to deal with missing data and censoring.

Depending on the overall sample size, subgroup analyses may be conducted for main study outcomes (eg, by country, by diagnosis).

Detailed methodology for summary and statistical analyses of data collected in this study will be documented in a SAP, which will be dated, filed, and maintained by the sponsor. The SAP may modify the plans outlined in the protocol; any major modifications of primary outcome definitions or their analyses would be reflected in a protocol amendment. The SAP will define all planned analytic populations and subpopulations, including definitions of overall response and AEs of interest. The SAP will further provide a detailed description of analyses to be performed.

Any known deviations from the planned analyses, the reason for such deviations and all alternative/additional statistical analyses that may be performed as well as the final statistical analysis must be described in a revised SAP before completion of data collection.

